**Table 6: Expected Surgical Adverse Events and Durations**

Event description	Time frame after the surgical procedure
Anesthesia-related nausea/vomiting	24 hours
Mild to moderate pain at surgical site	7 days
Low-grade fever (<100°F or < 37.8°C)	48 hours
Mild to moderate bruising / ecchymosis	7 days
Pocket site / incisional pain	14 days
Seroma	72 hours
Sleep problems (insomnia)	72 hours

## 11.7. Emergency Contact Details

For emergency contact regarding an SADE/DD, contact the Clinical Study Manager immediately. Refer to the country specific addenda for OUS information.

## 11.8. Deaths

The investigator must notify Medtronic immediately and the IRB/EC, as required, after learning of a subject's death, regardless of whether or not the death is related to the device system, therapy or procedure. The investigator should also attempt to determine, as conclusively as possible, whether such deaths are related to the device system, therapy, or procedure. If the death is evaluated as device-, therapy-, or procedure-related, and unanticipated, the event will be reported as a USADE by Medtronic to the appropriate regulatory authorities.

If it is determined that the cause of death was device-, therapy-, or procedure-related:

- And an autopsy is conducted, a copy of the report should be provided to Medtronic.
- Medtronic requests that all device system components that were being used at the time of the death be returned to Medtronic for analysis per Section 7.8.
- Requested death certificates and/or source documentation if obtained should be redacted and sent to Medtronic.
- If the death occurs at a location remote from the study site, it is the study site's responsibility to make three attempts to retrieve all pertinent information related to the subject's death and submit the investigator's death summary of the known events surrounding the death to Medtronic.

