## 11.3. Recording of Adverse Events

In this study, only device-, therapy- and procedure-related adverse events (AEs) and device deficiencies that occur from enrollment through subject discontinuation from the study will be collected. Adverse event and device deficiency information will be reported to Medtronic on an adverse event or device deficiency eCRF, one for each AE and/or device deficiency.

It is the responsibility of the investigator to identify the occurrence of device-, therapy- or procedure-related adverse events and device deficiencies and to ensure all required information is accurately recorded on the eCRF. Refer to the applicable eCRF for the information to be reported for each adverse event and device deficiency.

For adverse events that require immediate reporting, initial reporting to Medtronic may be done by phone, or e-mail, or on the eCRF by completing as much information as is available. The adverse event eCRF must be completed as soon as possible.

In case the investigator requires information from the sponsor in an emergency situation, the investigator can contact Medtronic using the contact details provided in the synopsis and Section 11.7.

The clinical course of each adverse event must be followed until the adverse event is resolved, the subject is in a stable condition, or until the subject discontinues from the study. "Ongoing" adverse events and device deficiencies must be assessed at each study visit. The adverse event eCRF should be updated when there is a change to the information provided on the form (e.g. change in intervention, outcome, relatedness, etc.).

At the last scheduled visit, the investigator will instruct the subject to provide an update on the status of any ongoing events and report any adverse event or issue with the device that they believe might be related to participation in the study.

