## 12. Data Review Committees

---

This study will not use a Clinical Events Committee (CEC), Adverse Events Advisory Committee (AEAC) or an independent Data Monitoring Committee (DMC). Instead, all reported adverse events and device deficiencies will be reviewed by a Medtronic Medical Advisor to ensure consistent reporting.

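### Protocol 11.8 asks for the records that would show whether a death was related only once the death has been determined to be related

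*Protocol*

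**What the plan says.** Protocol 11.8 has two layers.

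The first applies to every death. The investigator notifies the sponsor immediately, "regardless of whether or not the death is related to the device system, therapy or procedure". The section then adds: "The investigator should also attempt to determine, as conclusively as possible, whether such deaths are related to the device system, therapy, or procedure". It names no records to consult, no minimum evidence and no category for a death that cannot be resolved.

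The second layer is introduced by "If it is determined that the cause of death was device-, therapy-, or procedure-related" and contains four bullets: a copy of the autopsy report if an autopsy is done; return of the system components in use at death; a rule on documents, "Requested death certificates and/or source documentation if obtained should be redacted and sent to Medtronic"; and, where the death happened away from the site, "it is the study site's responsibility to make three attempts to retrieve all pertinent information related to the subject's death", together with submission of the investigator's death summary.

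What reaches the safety analysis is set elsewhere. Protocol 11.3 collects "only device-, therapy- and procedure-related adverse events (AEs) and device deficiencies that occur from enrollment through subject discontinuation", and Protocol 11.6 lists unrelated adverse events as not reportable. Protocol 12 provides no clinical events committee, adverse events committee or data monitoring committee; in their place, "all reported adverse events and device deficiencies will be reviewed by a Medtronic Medical Advisor to ensure consistent reporting". Protocol 13.6 and SAP 7.10 summarize the events so collected.

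**The concern.** The order is circular. Autopsy findings, a death certificate, hospital records and a written summary are what one would use to decide whether a death was related, yet the plan attaches them to deaths already decided to be related. The remote death is the clearest case: the site is least likely to hold any information, and its duty to look for it is switched on by a conclusion it may have no basis to reach.

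The relatedness judgement matters more here than in a trial that collects all adverse events. It decides whether a death enters the adverse event data at all, whether the Medical Advisor reviews it, and, if it is also unanticipated, whether it is reported to authorities as an unanticipated serious adverse device effect. At stake is the completeness of the most serious safety outcome in a study of an implanted system with no independent adjudication.

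**Working it through.** The plan states no figure on this point, so there is none to reproduce. The check is a reading of the provisions side by side, followed by an illustration of scale.

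**Step 1. Which duties depend on prior relatedness?**

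| Provision | Place | Conditional on relatedness? |
|---|---|---|
| Notify the sponsor of a death | Protocol 11.8 | No |
| Attempt to determine relatedness | Protocol 11.8 | No |
| Death as a reason on the study exit form | Protocol 9.19 | No |
| Investigator reports deaths to the sponsor | Protocol 15.8.2 | No |
| Return of explanted product, including from funeral homes | Protocol 7.8 | No |
| Autopsy report to the sponsor | Protocol 11.8 | Yes |
| Return of components in use at death | Protocol 11.8 | Yes |
| Certificates and source documents to the sponsor | Protocol 11.8 | Yes |
| Three retrieval attempts and death summary, remote death | Protocol 11.8 | Yes |

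The unconditional rows establish that a death occurred and ask for an opinion on its cause. Apart from the general return of explanted product, every row that supplies evidence on cause is conditional. Only the last row is a duty to go and retrieve information.

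**Step 2. Do other provisions reach a death not judged related?**

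- The Medical Advisor's review (Protocol 12) covers reported adverse events and device deficiencies. Unrelated events are not reportable (Protocol 11.6), so on the text such a death is not in that review.
- Sponsor queries and the procedure for recording disagreement (Protocol 11.5) also concern adverse events and device deficiencies notified to the sponsor.
- Monitors have direct access to source documents (Protocol 15.1 and 15.4), which may include autopsy reports. Access does not oblige anyone to obtain a record the site does not hold.

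**Step 3. Where would it appear in the outputs?**

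- The SAP 7.10 tables summarize collected events, that is, related ones. The legible text has no table or listing of all deaths.
- The SAP 7.1.1 disposition table counts subjects at each visit. It does not specify reasons for exit or a death count.

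So a death not judged related has no place in the legible planned safety tables.

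**Step 4. Scale, for illustration.** The documents give no expected death rate. Assume one death is left out. The denominators are 100 (the target number reaching the 3-Month Visit, used here for treated subjects) and 215 (maximum enrolled). The interval is the Wilson score interval that SAP 7.2 names for percentages of subjects, with z = 1.96:

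limits = [p + z²/(2n) ± z√(p(1−p)/n + z²/(4n²))] / (1 + z²/n)

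For x = 0 the upper limit reduces to z²/(n + z²): 3.84/103.84 = 3.7% at n = 100, and 3.84/218.84 = 1.8% at n = 215.

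For x = 1, n = 100: centre (0.01 + 0.0192)/1.0384 = 0.0281; half-width 1.96 × √(0.000099 + 0.000096)/1.0384 = 0.0264; limits 0.2% to 5.4%.

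| Deaths shown / n | Estimate | Wilson 95% interval |
|---|---|---|
| 0/100 | 0% | 0% to 3.7% |
| 1/100 | 1.0% | 0.2% to 5.4% |
| 0/215 | 0% | 0% to 1.8% |
| 1/215 | 0.5% | 0.1% to 2.6% |

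This shows what one omitted death would do. It does not show that the clause will cause an omission.

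**The case against.** The strongest reply is that 11.8 already asks for a determination that is as conclusive as possible for every death, and an investigator who takes that seriously will seek records whatever the bullets say. Nothing forbids obtaining them earlier. The autopsy and certificate bullets mainly govern what is forwarded to the sponsor, and return of explanted product is requested in Protocol 7.8 without any relatedness condition. Deaths are notified, reported and recorded at exit, and monitors can see source documents. All of this stands. It confines the retrieval problem to the remote-death bullet and makes the others a question of what the sponsor receives.

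A reader might infer more, in three ways that the documents do not support:

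- *That an unresolved death is classed as unrelated.* No such default is stated. What is missing is any rule for undetermined relatedness.
- *That the sponsor has nothing with which to check the judgement.* It has the notification, the exit form and monitoring access. What it lacks is an assured set of records and a review that formally covers the death.
- *That errors can only lower the count.* An investigator without records might also attribute a death to the implant out of caution. The documents give no evidence on direction. What can be said is that any related death left unjudged or judged unrelated would be missing from the tables.

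The objection also notes that changing the lead-in alone would not bring an undetermined death into a related-only table. That is right, and the fix allows for it.

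**Conclusion.** The point holds as a defect in the order of the rules. The retrieval duty for a remote death, and the forwarding of death records to the sponsor, are conditional on a conclusion those records should inform. Undetermined relatedness is not addressed, and a death not judged related lies outside the Medical Advisor's review and outside every legible planned safety table.

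The size is modest. No primary or secondary efficacy result is affected. Few deaths are likely; 0 to 3 among up to 215 enrolled is an assumption, not a figure from the documents. One death among 100 treated subjects separates 0% (upper limit 3.7%) from 1% (upper limit 5.4%).

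Two limits apply. Parts of the SAP are redacted, and geography-specific addenda were not available, so a death listing or a further reporting rule there cannot be excluded. This is a cheap improvement to safety ascertainment, not a flaw that threatens the study's conclusions.

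**What to change.** 1. In Protocol 11.8, replace the lead-in to the four bullets with: *For every subject death, regardless of presumed cause:* and reword the opening of the autopsy bullet to fit. The bullets then apply before relatedness is decided, and their scope matches the notification rule.
2. In Protocol 11.8 or 12, have the Medical Advisor record a relatedness opinion on each death from those documents, with *undetermined* allowed as a category alongside related and not related.
3. In SAP 7.10, add an all-cause death count or a listing by study phase, showing the investigator's and the Medical Advisor's classification. Without this step the first two would not reach the report.

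The cost is a changed lead-in, one or two added sentences in the Protocol and one short output in the SAP, using existing roles. The downside is document retrieval for the few deaths first thought unrelated. No treatment or visit changes.

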## 12. Data Review Committees

---

This study will not use a Clinical Events Committee (CEC), Adverse Events Advisory Committee (AEAC) or an independent Data Monitoring Committee (DMC). Instead, all reported adverse events and device deficiencies will be reviewed by a Medtronic Medical Advisor to ensure consistent reporting.

## 13. Statistical Design and Methods

---

### 13.1. General Statistical Considerations

Data analysis will be performed by Medtronic-employed statisticians or designees. A validated statistical software package (e.g., SAS version 9.4 or higher) will be used to analyze the study results.

The Statistical Analysis Plan (SAP) will be developed prior to data analysis and will include a comprehensive description of the statistical methods and reports to be included in the final study report. Any change to the data analysis methods described in the CIP will require an amendment only if it changes a principal feature of the CIP. Any other change to the data analysis methods described in the CIP, and the justification for making the change, will be described in the clinical study report.

All analyses will be pooled by neurostimulator model unless otherwise specified.

PASS11 was used to calculate the sample size for the primary objective.

### 13.1.1. Analysis populations

There will be 4 population sets for the purposes of analysis in this study:

**Enrolled Analysis Set:** All consented subjects.

**Trialed Analysis Set:** All subjects who are implanted with trialing leads at T9/T10 and programmed at the Device Trial Day 0 Visit.

**Implanted Analysis Set:** All subjects who have a positive device trial with HD parameters at T9/T10 and are implanted with a neurostimulation system.

**Treated Analysis Set:** All subjects in the Implanted Analysis Set whose devices are activated at the Device Activation Visit.

### 13.1.2. Handling of missing data

The primary and secondary efficacy objectives will be evaluated for the Treated Analysis Set. For subjects in the Treated Analysis Set with missing outcome data, the missing outcome measure will be imputed using multiple imputations (MI). [REDACTED]

[REDACTED]

Following imputation, the objectives will be evaluated using MI analysis methods.

Imputation for missing data may be implemented for the long-term additional measures analyses.

### 13.1.3. Interim efficacy analyses

An interim analysis providing preliminary characterization of the secondary objectives will be performed in late 2018 with the intent of presenting the results in early 2019. The details of these analyses will be specified in the SAP.

Analyses of the efficacy outcomes and safety assessment will be performed after 100 subjects have reached the 3-Month Visit, as described in section 13.1.6. The primary efficacy objective will not be evaluated. These analyses will be specified in the SAP and are not intended to be used to modify the study.

### 13.1.4. Center pooling

All investigators in the proposed study will conduct the study according to a common protocol and utilize the same CRFs to collect study data. In addition, site study personnel training will be conducted prior to initiation of the study in each site and periodic monitoring will be conducted by Medtronic to ensure compliance with protocol requirements.

Data will be pooled across centers for all analyses. No single site will be allowed to implant more than 25 subjects. This is intended to reduce the possibility that a site with atypical results will be overly influential in the study results based on pooled data.

### 13.1.5. Multiple testing adjustment

The study has one primary objective that will be evaluated with statistical testing. The primary objective will be evaluated at an alpha level of 0.05 after all subjects in the Treated Analysis Set have completed the 3-Month Visit.

Therapy efficacy will be demonstrated by successfully passing the primary objective analysis. The secondary objectives are not alpha-controlled; they will be characterized but not evaluated with statistical testing.

### 13.1.6. Reports

[REDACTED]

## 13.2. Demographics

Demographics and baseline characteristics will be summarized for all enrolled subjects, as well as the subset of subjects in the Treated Analysis Set.

## 13.3. Primary Objective

### 13.3.1. Primary objective

To demonstrate a significant improvement in overall (low back and leg) pain intensity using HD stimulation starting at 90 - 200  $\mu$ sec and 1000 Hz with lead placement spanning the T9/T10 disc space, as measured by the Visual Analog Scale (VAS), from Baseline to the 3-Month Visit.

### 13.3.2. Hypothesis

The mean change in overall pain in implanted subjects ( $\mu_c$ ) from baseline to 3 months will be statistically significantly different from no change on the VAS scale 0-100 mm:

$$H_0: \mu_c = 0$$

$$H_A: \mu_c \neq 0$$

### 13.3.3. Endpoint definition

The change in overall pain will be calculated for all subjects in the Treated Analysis Set as:

$$\text{Baseline overall pain} - \text{3-Month overall pain}$$

The baseline and 3-month overall pain scores will be collected on the Visual Analog Scale (VAS) at the Baseline and 3-Month Visits, respectively.

### 13.3.4. Study sample size justification

The Tests for One Mean in PASS11 was used to calculate the sample size. The assumptions of  $\alpha = 0.05$ , power = 0.9, null mean (Mean0) = 0, alternative mean (Mean1) = 20, standard deviation = 30, alternative hypothesis = Mean0  $\neq$  Mean1, and Infinite population size, results in a sample size of 26 subjects. However, a sample size of 100 subjects derived for the secondary objectives (section 13.4) ensures over 99% power under those same assumptions.

Up to 215 subjects will be enrolled to ensure at least 100 subjects reach the 3-month endpoint.

### 13.3.5. Analysis methods

The two-sided, one sample t-test will be used to test the hypothesis of the primary objective. The main analysis will include all subjects in the Treated Analysis Set. In addition to the hypothesis test, the two-sided 95% confidence interval for the average change in overall pain will be calculated and reported.

### 13.3.6. Handling of missing data

The primary analysis for this efficacy objective will be evaluated for all subjects in the Treated Analysis Set. The method for handling missing data for the primary endpoint is described in section 13.1.2.

### 13.3.7. Sensitivity analyses

Sensitivity analyses will be conducted for the primary efficacy objective using the methods described below:

- Completers analysis:
  - Only subjects in the Treated Analysis Set with complete paired data at the Baseline and 3-Month Visits will be included in the analysis.

█ [REDACTED]

█ [REDACTED]

[Redacted]

[Redacted]

## 13.4. Secondary Objectives

### 13.4.1. Secondary objective 1: Overall pain responder rate

To characterize the overall (low back and leg) pain efficacy responder rate, as measured by the VAS, from Baseline to the 3-Month Visit, with a confidence interval within  $\pm 10\%$ .

#### Endpoint definition

The responder rate will be calculated as the proportion of subjects in the Treated Analysis Set who demonstrate at least a 50% improvement in overall pain from baseline to 3 months. For each subject, percentage improvement will be calculated as:

$$\frac{(\text{Baseline overall pain} - \text{3-Month overall pain}) \times 100}{\text{Baseline overall pain}}$$

The baseline and 3-month overall pain scores will be collected on the VAS at the Baseline and 3-Month Visits, respectively. Subjects who report at least a 50% improvement in overall pain will be considered responders.

#### Study sample size justification

Calculations were performed using PASS11, Confidence Intervals for One Proportion, with Confidence Level = 0.95, P = 0.5, Confidence Interval Formula = Score (Wilson), Interval Type = Two-Sided. Table 7 shows the 95% confidence interval for a 50% responder rate for 50-100 subjects. A sample size of 100 subjects provides a 95% confidence interval within 9.6% of the responder rate estimate, if the observed responder rate is 50%. The confidence interval is the widest with a responder rate of 50%; a lower or higher responder rate will have a narrower confidence interval.

**Table 7. 95% Confidence Interval (CI) for Responder Rate = 50%**

N	Lower Limit	Upper Limit	CI Width	+/- Range
50	36.6%	63.4%	26.7%	13.4%
60	37.7%	62.3%	24.5%	12.3%
70	38.6%	61.4%	22.8%	11.4%
80	39.3%	60.7%	21.4%	10.7%
90	39.9%	60.1%	20.2%	10.1%
100	40.4%	59.6%	19.2%	9.6%

## Analysis methods

The responder rate as defined above will be calculated for subjects in the Treated Analysis Set. The score (Wilson) method will be used to calculate the 95% confidence interval of the responder rate. In this analysis, missing data will be imputed as described above in section 13.3.6. Sensitivity analyses will be performed as described in section 13.4.4.

### 13.4.2. Secondary objective 2: Low back pain responder rate

To characterize the low back pain efficacy responder rate, as measured by the VAS, from Baseline to the 3-Month Visit, with a confidence interval within  $\pm 10\%$ .

#### Endpoint definition

The responder rate will be calculated as the proportion of subjects in the Treated Analysis Set who demonstrate at least a 50% improvement in low back pain from baseline to 3 months. For each subject, percentage improvement will be calculated as:

$$\frac{(\text{Baseline low back pain} - \text{3-Month low back pain}) \times 100}{\text{Baseline low back pain}}$$

The baseline and 3-month low back pain scores will be collected on the VAS at the Baseline and 3-Month Visits, respectively. Subjects who report at least a 50% improvement in low back pain will be considered responders.

#### Study sample size justification

Calculations were performed using PASS11, Confidence Intervals for One Proportion, with Confidence Level = 0.95, P = 0.5, Confidence Interval Formula = Score (Wilson), Interval Type = Two-Sided. Table 8 shows the 95% confidence interval for a 50% responder rate for 50-100 subjects. A sample size of 100 subjects provides a 95% confidence interval within 9.6% of the responder rate estimate, if the observed responder rate is 50%. The confidence interval is the widest with a responder rate of 50%; a lower or higher responder rate will have a narrower confidence interval.

